### **13. ETHICAL ASPECTS RELATED TO THE TRIAL**

All parties involved in this trial undertake to strictly observe the Good Clinical Practice guidelines and the ethical considerations set forth by the current Spanish Legislation governing clinical trials, as well as the corresponding recommendations derived from the European Legislation, as specified in point 3.7 of this protocol.

To ensure the subjects' rights, the Principal Investigator or the associate investigators will explain the trial's objectives and requirements, the nature of the medicinal product under study, and its possible side effects, in a language understandable to the Subject, in the Subject information sheet. The information to be provided includes: a description of the trial objectives, the methodology to be used, the type of treatment, the benefits that the Subject may obtain from the treatment, the risks to which they may be exposed, and the right to withdraw from the trial if they wish to do so.

All subjects must provide their written informed consent before being included in the trial. The informed consent forms shall be stored by the investigator in the trial file during the course of the trial and thereafter for the time stipulated by the legislation in force (at least 15 years).

The research staff will ensure that the relevant consent form is completed according to the subject's age.

### **14. DATA PROCESSING AND FILING**

Inmunotek, S.L. will provide the CRFs that must be fully completed and legible. Any omission of data must be justified in all cases. The member of the research team responsible for making corrections in the cited forms must write their initials and the date on which the correction was made in the location of the amendment.

[name]  
Traductor-Intérprete Jurado de INGLÉS  
Nº 9971

The investigator shall submit a list with the signature and handwritten initials of each of the collaborators authorized to make data entries or changes in the case report forms. If any modification is made throughout the course of the study, an updated list of authorized signatures must be provided.

Subject data recorded in the CRFs during the course of the trial must be documented in an anonymous manner, exclusively identifying the subject by their assigned number. If the subject needs to be identified due to exceptional safety reasons or by indication of the Regulatory Authorities, the investigator will be obliged to maintain the confidentiality of such information.

The investigator must retain the original documents for each trial subject comprising all demographic and medical information, including laboratory data, and keep a copy of the signed informed consent form. All information recorded in the CRFs must be traceable to the original documents stored in the subject's file. Data without an original written or electronic record will be defined before the start of the trial and directly recorded in the CRFs, where they will be documented as original data.

The investigator must safeguard and maintain the essential documents defined by the ICH guidelines, the Good Clinical Practice guidelines, and the local regulations for at least 15 years following the trial's termination or completion. The Subjects' medical records and other original data will be retained for the maximum time permitted by the hospital. To this end, the sponsor shall provide the investigator with a file, which the investigator must update as often as necessary.

The investigator's file must be accessible during monitoring visits, and in case of an audit and/or inspection.

Inmunotek, S.L. is responsible for the updated master file of all documentation relating to the trial and must keep all this information during the entire shelf life of the medicinal product. Any change in the data ownership must be documented. In all cases, the documents must be made available to the competent authorities if so requested by them. Once the trial period has ended for each subject, the trial monitor will collect their case report form, which they will subsequently review, recording any

discrepancy, concern, or comment about it in a separate document. The monitor shall discuss this list of discrepancies with the investigator in order to correct the corresponding data in the case report form. Any corrections resulting from this discussion must be made by the authorized research staff. Neither the trial monitor nor any delegate of Inmunotek, S.L. is authorized to enter data or make corrections in the case report forms.

Upon completion of this review, the data corresponding to all the subjects included in the trial will be computerized, using a double data entry system, for their subsequent statistical analysis. Once processed, the original forms will be filed together with all relevant trial documentation in the Medical Department of Inmunotek, S.L. This file will be clearly identified in case its review or audit is required.

## **15. FINANCING AND INSURANCE**

Inmunotek, S.L. has taken out a Civil Liability insurance policy in accordance with the current legislation.

## **16. PUBLICATION POLICY**

The results or conclusions derived from this trial shall preferably be disclosed in scientific publications referencing the corresponding Ethics Committee. The anonymity of the subjects participating in the trial shall be maintained at all times.

The partial or full publication or disclosure of the data or conclusions obtained from the clinical trial will be performed by mutual agreement between the investigator and Inmunotek, S.L. If the Trial Sponsor fails to do so within one year, the investigators will be free to publish the results obtained in the trial.

## 17. ANNEXES

N/A

HGUGM	Hospital General Universitario Gregorio Marañón
HCSC	Hospital Clínico San Carlos
CRF	Case Report Form
CAT	COPD ASSESSMENT TEST
ELISA	Enzyme Linked ImmunoSorbent Assay
GCP	Good Clinical Practice
IgAs	Secretory Immunoglobulin A
IMP	Investigational Medical Product
ITT	Intention To Treat Set or Population
LNs	Local/regional mucosa-draining lymph Nodes
MALT	Mucosa-Associated Lymphoid Tissue
NKs	Natural Killer cells
PHA	Phytohemagglutinin
PIDs	Primary ImmunoDeficiencies
PP	Per Protocol Set or Population
RRTIs	Recurrent Respiratory Tract Infections
SAE	Serious Adverse Event
SAP	Statistical Analysis Plan
SUSARs	Suspected Unexpected Serious Adverse Reactions

1. *Revisions*

2. *Introduction*

2.1. *Preface*

This statistical analysis plan (SAP) describes all planned analyses for the Clinical Study Report (CSR) of study MV130-SLG-001, a prospective, randomized, double-blind, parallel, placebo-controlled clinical trial evaluating the safety, clinical efficacy, and immunomodulatory response of a polyvalent bacterial vaccine (Bactek[®]) administered via the sublingual mucosa in subjects with chronic obstructive pulmonary disease (COPD).

The content of this SAP is based on protocol MV130-SLG-001 Amendment version 8. All decisions regarding final analysis, as defined in the SAP document, have been made prior to database lock of the study data.

Other endpoints, including immunological substudies, as well as other potential future analyses of data arising from this trial, will be the subject of future analysis plans.

2.2. *Scope of the analyses*

These analyses will assess the efficacy and safety of MV130 in comparison with placebo and will be included in the clinical study report. This statistical analysis plan (SAP) will give more detailed descriptions of the endpoints in the study and the corresponding analyses.

3. Trial Objectives

3.1. Primary Objective

The main objective of this trial is to evaluate the efficacy of a bacterial vaccine administered sublingually compared to placebo in subjects with moderate and severe COPD based on the number of COPD exacerbations.

3.2. Secondary Objectives

The secondary objective of this trial is to evaluate the impact of the investigational medicinal product on the following parameters:

- ★ Severity of the COPD exacerbations.
- ★ Time elapsed between the start of the treatment and the first COPD exacerbation.
- ★ Use of drugs (antibiotics, corticosteroids, etc).
- ★ Number of medical consultations due to COPD exacerbations.
- ★ Number of visits to the Emergency Department resulting or not in hospitalization.
- ★ Number of hospitalizations due to COPD exacerbations.
- ★ Days of hospitalization due to COPD exacerbations.
- ★ Health-related quality of life, as determined by an adapted version of a specific quality of life questionnaire: the COPD Assessment Test (CAT).
- ★ Healthcare expenditure resulting from resource consumption during episodes of COPD exacerbations occurring during the trial period.
- ★ Variations (change between the baseline level and months 0, 3, 6, and 12, as well as in comparison with the placebo) in the following immunological parameters in the patients participating in the substudy (N = 60) and/or those of the induced sputum study (N = 20) (between month 0 prior to the administration of the vaccine and month 12):
 - Specific humoral response [REDACTED]
 - Specific cellular response [REDACTED]

In a subgroup of patients (n = 20) selected from the group of patients participating in the immunological substudy (n = 60), a genetic study consisting in an evaluation performed at month (M) 0 (visit 1) and month 12 following the start of the vaccination will be performed on samples of induced sputum to study the following:

- ★ mRNA and miRNA expression profiles in PBMCs.
- ★ Proteomics using the iTRAQ technique.
- ★ Phenotypic markers of leukocyte populations.
- ★ Neutrophil function studies: phagocytosis (Phagotest) and bacteriophage capacity of the neutrophils (oxidative burst).
- ★ The first subgroup of subjects (N = 60) will be recruited from the [REDACTED] hospitals. The subgroup of subjects on which the induced sputum study will be performed (N = 20) (selected from the group of 60 subjects described above) will be recruited from the [REDACTED] hospital.
- ★ Safety outcomes
 - Overall rate, severity, and relationship of any adverse event (AE) per administration and patient.
 - Assessment of local tolerability (tissular reactions in the administration site).
 - Changes in standard laboratory parameters (serum chemistry and hematology).

4. Trial Design

This is a Phase II/III, prospective, multicenter, randomized, double-blind, parallel, placebo-controlled clinical trial where participants were administered sublingual bacterial vaccine or placebo during 12 months and were followed during an additional 6 months.

4.1. Study Assessments

Table 1 shows procedures to be followed during the study.

Table 1 Overview of the Trial Design, Procedures, and stages

VISIT No.	Baseline	1	2	3	4	5	6
		0	3	6	12	15	18
Period window		±10 days					
Informed consent	✓						
Inclusion/exclusion criteria	✓						
Demographic data (including area of residence)	✓						
Vital signs (BP and HR)	✓						
Tobacco consumption (no. of cigarettes/day ✓ no. of years/20)	✓	✓	✓	✓	✓	✓	✓
Medical history/complete examination	✓	✓	✓	✓	✓	✓	✓
Exhaled CO	✓	✓	✓	✓	✓	✓	✓
Hematology	✓			✓	✓		✓
Serum chemistry	✓			✓	✓		✓
Viral serology testing (HBV, HCV, and HIV)	✓				✓		✓
Complete immunological evaluation	✓			✓	✓		✓
Immunological substudy (N = 60)		✓	✓	✓	✓		✓
Immunological substudy with induced sputum (N = 20)		✓			✓		
Spirometry	✓				✓	✓	✓
Recording of concomitant medication	✓	✓	✓	✓	✓	✓	✓
Pregnancy test	✓						
Recording of healthcare resource consumption	✓	✓	✓	✓	✓	✓	✓
Randomization no.		✓					
No. of days of antibiotic treatment required		✓	✓	✓	✓	✓	✓
Subject's visual analog scale score	✓	✓			✓	✓	✓
Investigator's visual analog scale score	✓	✓			✓	✓	✓

Quality of life questionnaire	✓	✓	✓	✓	✓	✓	✓
Provision of the patient diary		✓	✓	✓	✓		
Collection of the patient diary			✓	✓	✓		
Delivery of the sublingual vaccine		✓	✓	✓			
Collection of the sublingual vaccine			✓	✓	✓		
Recording of the no. of days of hospitalization		✓	✓	✓	✓	✓	✓
Recording of adverse events		✓	✓	✓	✓	✓	✓
Recording of unscheduled visits		✓	✓	✓	✓	✓	✓
Recording of trial dropout/termination cause		✓	✓	✓	✓		
Comments	✓	✓	✓	✓	✓	✓	✓
CRF review	✓	✓	✓	✓	✓	✓	✓

5. Trial Population

5.1. Population description

Three analysis sets are defined, the Full Analysis Set (FAS), the Per Protocol Analysis Set (PP) and the safety analysis set.

5.1.1. Safety Analysis Set

The Safety Analysis Set will consist of all subjects that are enrolled and receive at least 1 dose of MV-130. The safety analysis set comprises all randomized subjects.

5.1.2. Intention to Treat Set or Full Analysis Set (FAS)

All randomized subjects who have taken at least one dose. These subjects will be assigned to the corresponding treatment group.

5.1.3. Per Protocol Analysis Set (PP)

Randomized subjects completing the 50-week efficacy assessment period and adequately complying with the protocol. These subjects will be assigned to the actual treatment group. Any significant deviation from the treatment schedule will result in an exclusion from the "per-protocol" dataset.

5.2. Inclusion–Exclusion Criteria and General Study Population

A total of 198 subjects will be screened from the Respiratory Departments of participating centers.

These screened subjects will have been diagnosed with moderate or severe COPD.

5.2.1. Subject Inclusion Criteria

A COPD exacerbation will be considered to be recurrent when it occurs at a frequency of at least three episodes in one year.

In this study we will include subjects who meet the following criteria:

- ★ Subjects who have provided their written informed consent.
- ★ Subjects of both sexes.
- ★ Subjects aged between 35 and 85 years.
- ★ Subjects who are capable of complying with the dosing regimen.
- ★ Subjects with a diagnosis of moderate or severe COPD according to the GOLD criteria.
 - Subjects with a predicted post-bronchodilator force expiratory volume in the first second (FEV₁) <50% (50% - 30%), with or without chronic symptoms (e.g., coughing or sputum production).
- ★ Subjects who have experienced at least three moderate exacerbations (i.e., those requiring treatment with antibiotics, systemic corticosteroids, or both, as prescribed by their general practitioner or pulmonologist in the standard consultation and/or the Emergency Department of their Clinic) or two exacerbations with at least one requiring hospitalization due to a COPD exacerbation and the other one a moderate exacerbation occurred within the last year.
- ★ Subjects who have not changed their medication for the maintenance treatment of COPD within the past 6 months.
- ★ Subjects with an accumulated consumption of ten or more pack-years. The subjects may or may not be active smokers.
- ★ Subjects included in the trial may have been vaccinated with pneumococcal polysaccharide vaccine at least 4 weeks before starting the administration of Bactek®.
- ★ Women of childbearing age must use an approved method of contraception (oral, vaginal, transdermal, intrauterine device [IUD], etc. or barrier methods) and obtain a negative result in the urine pregnancy test performed during the screening visit.

5.2.2. Subject Exclusion Criteria

- ★ Subjects outside the allowed age range.
- ★ Subjects who are unable to cooperate and/or have a severe psychiatric disorder.
- ★ Women who are pregnant, breastfeeding, expect to become pregnant during the study (including assisted reproduction), or who refuse to use contraceptives during the study (including barrier methods). Women who become pregnant during the

clinical trial will have to discontinue their participation in it.

- ★ Subjects who have participated in a study or clinical trial with an investigational product within the 3 months preceding their inclusion in this study.
- ★ Subjects diagnosed with asthma based on the guidelines of the American Thoracic Society and the European Respiratory Society. If the investigators are unable to differentiate between COPD and asthma after applying the criteria listed in the following table, a bronchodilator test with inhaled salbutamol must be performed, excluding those subjects with FEV1 changes >400 mL.

Medical History	COPD	ASTHMA
Smoker or ex-smoker	Almost all	Possible
Onset of symptoms <35 years	Rare	Common
Chronic productive cough	Common	Uncommon
Dyspnea	Persistent and progressive	Variable
Waking up in the middle of the night with dyspnea and wheezing noises	Uncommon	Common
Significant daytime or daily symptomatology changes	Uncommon	Common

- ★ Subjects with a diagnosis other than COPD that causes them to have an unstable condition or a life expectancy <3 years.
- ★ Subjects who experienced a COPD exacerbation within 4 weeks prior to the start of the trial.
- ★ Subjects with moderate COPD who required treatment with inhaled corticosteroids in the last 4 weeks.
- ★ Subjects with moderate COPD who received systemic corticosteroids (orally, intramuscularly, or intravenously) in the last 4 weeks.
- ★ Subjects diagnosed with a Primary (European Society for Immunodeficiencies [ESID] guidelines) or Secondary Immunodeficiency within the 12 months preceding their inclusion in the clinical trial or the trial's baseline visit.
- ★ Subjects diagnosed with a chronic lymphoproliferative disease.
- ★ Subjects diagnosed with a chronic infectious disease (tuberculosis [TB], HCV, HIV, or HBV).
- ★ Subjects with chronic heart disease, arrhythmias, or episodes of arrhythmia secondary to the use of bronchodilators.
- ★ Subjects diagnosed with COPD and chronic colonization by *Pseudomonas aeruginosa*.
- ★ Subjects with COPD and bronchiectasis diagnosed by CT imaging before the age of 40.
- ★ Subjects diagnosed with very severe COPD according to the GOLD classification.
- ★ Subjects requiring home oxygen therapy or non-invasive mechanical ventilation.
- ★ Subjects with a history of hypersensitivity to any of the vaccine's components.
- ★ Subjects receiving immunosuppressive treatment with: azathioprine, methotrexate, cyclosporin, cyclophosphamide, tacrolimus, antimarial drugs, or gold salts.
- ★ Subjects who have been treated with monoclonal antibodies such as rituximab or TNF-alpha inhibitors in the last 6 months.
- ★ Subjects receiving chronic treatment with azithromycin or inhaled antibiotics (tobramycin or colistin).

6. Endpoints

6.1.1. Primary outcome

The primary efficacy outcome is a decrease in the mean number of COPD exacerbations. A clinical diagnosis of an exacerbation according to the GOLD definition will be considered; that is, an event occurring throughout the natural course of the disease, characterized by a change of acute onset, beyond the daily variability, in the patient's dyspnea, cough, and/or expectoration, which may require a change in the patient's usual medication.

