#### **5.6. Description of the Subject “Termination Criteria” and “Discontinuation Criteria” During the Entire Trial or Parts of It**

The trial shall end with the trial's database lock.

Subjects may temporarily discontinue the treatment for 7 to 14 days in any of the following cases:

- Severe or very severe COPD exacerbation.

Acute exacerbations will be graded according to the following scale:

1. Mild (home care with or without contact with the subject's doctor).
2. Moderate (requiring a visit to the Emergency Department).
3. Severe (requiring hospitalization).
4. Very severe (requiring intubation and mechanical ventilation).

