### **10. STATISTICS**

#### **10.1. Description of the Statistical Methods to be Used, Including the Schedule of any Planned Interim Analysis**

The study analysis will be performed after the database lock. The intention-to-treat (ITT) population will be composed of subjects who took at least one dose of the trial medication. The analysis will be performed on both the ITT and per-protocol populations.

The randomization will be evaluated by comparing the baseline variables (month 0) in both study groups according to the Consolidated Standards of Reporting Trials (CONSORT) due to their clinical relevance. Qualitative variables will be reported together with their frequency distribution, and quantitative variables will be reported together with their mean and standard deviation, or, in case of asymmetry, with their median and interquartile range. If confounding is detected, the effects will be adjusted with the potentially confounding variables using the appropriate model adjustments.

The following variables will be analyzed to determine whether they follow a normal distribution: number of exacerbations, duration of the episodes, need for antibiotic therapy, number of hospital admissions, duration of the hospital admissions, immunological outcomes described in the trial design (page 67), quality of life, and direct costs.

These variables will be described together with their mean and standard deviation, or, in case of asymmetry, with their median and interquartile range. Differences between the means will be analyzed using Student's T test in the case of variables with a normal distribution and Mood's median test in the case of variables without a normal distribution. The absolute effect (difference in estimators) and its precision will be estimated with a 95% confidence interval (CI) in all cases.

The rate of exacerbations per patient and the severity of these exacerbations will be compared using the chi-square test or Fisher's exact test. The relative risks will be estimated together with their 95% CI. The number needed to treat (NNT) or number of events prevented per treatment will be estimated.

The rate of episodes occurred over time will be calculated, and the hazards ratio (HR) will be estimated together with its 95% CI following a Cox proportional-hazards model. The NNT (number of patients that need to be treated to avoid an event) will also be estimated.

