7.1.1. Sample Size and Power

The calculation of the sample size is based on the efficacy measured based on the decrease in the number of episodes of COPD exacerbations during the 12-month treatment period of the trial per subject.

The ratio of subjects to be distributed among the active treatment and placebo groups will be 1:1.

We estimate that subjects from group I (active treatment with the bacterial vaccine) will achieve a 60% decrease in their number of COPD exacerbations compared with a 30% decrease among those of group II (placebo). With an alpha error of 0.05 and a beta error of 0.2, and assuming a dropout rate of 20-25%, the number of subjects to be recruited would be 90 per study group, with an overall total of 180 trial subjects.

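### The primary outcome and sample size are a decrease with no stated reference period, and the only pre-entry count in the documents uses a narrower event definition than the on-trial count

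*SAP*

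**What the plan says.** **Outcome.** SAP 6.1.1, matching Protocol 5.1, states: "The primary efficacy outcome is a decrease in the mean number of COPD exacerbations". An on-trial event is a GOLD clinical diagnosis of acute worsening "which may require a change in the patient's usual medication", so treatment is possible but not required.

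**Sample size.** SAP 7.1.1, matching Protocol 10.2, counts episodes per subject over the 12 months of treatment and assumes that the vaccine arm "will achieve a 60% decrease in their number of COPD exacerbations compared with a 30% decrease among those of group II (placebo"). With alpha 0.05, beta 0.2 and 20–25% dropout it arrives at 90 per arm. It gives no reference period, baseline rate or measure of variability.

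**Pre-entry count.** SAP 5.2.1 and Protocol 6.1 require, within the last year, "at least three moderate exacerbations (i.e., those requiring treatment with antibiotics, systemic corticosteroids, or both"), or two events of which one led to hospital admission and the other was moderate.

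**Severity grades.** Protocol 5.6 has a different scale, with "Mild (home care with or without contact with the subject's doctor") below "Moderate (requiring a visit to the Emergency Department").

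**Analysis.** SAP 7.1.9 names a median or Mann-Whitney test for the primary endpoint and lists Poisson regression with baseline covariates under secondary endpoints. SAP 7.4.1 places a robust Poisson model, with follow-up time as exposure where it varies, under the primary analysis. SAP 7.1.7 says that all baseline characteristics will be used but lists none. Protocol 10.1 says: "If confounding is detected, the effects will be adjusted with the potentially confounding variables using the appropriate model adjustments".

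**The concern.** A placebo arm can show a 30% decrease only against its own past, so the sizing statement implies a pre-entry reference. The one such count in the documents is the eligibility count, and it covers fewer kinds of event than the on-trial count. Measured against it, a patient could appear to worsen only because milder events are now counted.

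Two things are at stake. First, the figures on which the trial is sized, and any within-arm decrease that is later reported, would mix treatment effect, change of definition and selection for a bad year. Second, the prior-year count is likely to predict the on-trial count, yet nothing guarantees that it enters the primary estimate. SAP 7.1.9 names an unadjusted test, and the adjusted model is called primary in one section and secondary in another.

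**Working it through.** **1. The plan's own figure.** 90 per arm does not follow from the stated inputs.

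- Read as proportions, 0.60 vs 0.30, two-sided: n = [1.96·√(2·0.45·0.55) + 0.842·√(0.24 + 0.21)]² / 0.30² = 42 per arm. Dividing by 0.80 or 0.75 for dropout gives 53 or 56. With 72 evaluable (90 × 0.80) the power would be 95.9%, not 80%.
- Read as mean percentage decreases, 90 per arm requires an SD of about 62–64 percentage points, which is not stated.
- Read as rates 0.7B vs 0.4B, with prior rate B and negative binomial dispersion k: n = (1.96 + 0.842)²·(1/0.7B + 1/0.4B + 2k) / [ln(0.4/0.7)]². After 20–25% dropout this gives 73–78 (B = 3, k = 0.5), 104–111 (B = 3, k = 1) and 94–100 (B = 2, k = 0.5).

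So 90 is plausible as a rate comparison but cannot be derived without a baseline rate and dispersion. B and k here are assumptions.

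**2. Size of the definition mismatch.** Let d be the true like-for-like decrease in treated events and f the share of on-trial GOLD events that are treated. Then apparent decrease = 1 − (1 − d)/f.

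| f (assumed) | d = 30% (placebo) | d = 60% (vaccine) |
|---|---|---|
| 0.90 | 1 − 0.70/0.90 = 22% | 1 − 0.40/0.90 = 56% |
| 0.80 | 1 − 0.70/0.80 = 12.5% | 1 − 0.40/0.80 = 50% |
| 0.70 | 1 − 0.70/0.70 = 0% | 1 − 0.40/0.70 = 43% |

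The documents do not give f. The closest figure is in Protocol 3.2, which reports antibiotic prescription in over 90% of COPD exacerbations in Spain. That points to the first row, but it describes routine care, not this endpoint.

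**3. Effect on the between-arm comparison.** If untreated events respond to the vaccine as treated ones do, the rate ratio is 0.40/0.70 = 0.571 at every f. If they do not respond at all, the ratio is 0.571·f + (1 − f): 0.614, 0.657 and 0.700 for f = 0.90, 0.80 and 0.70. With 72 per arm, B = 3 and k = 0.5, power then falls from 88% to 81, 72 and 61%. That is dilution from a wide endpoint, not bias, and the documents do not say how untreated events respond.

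**4. Selection.** Patients enter because their last year was bad. In gamma-Poisson simulations with entry at three or more events, assumed population mean rates of 1.5–3 per year and rate variance 0.3 or 0.6, the count fell by 16–42% with no treatment effect.

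**5. What the prior-year count buys.** Power in the same type of simulation:

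- At a rate ratio of 0.55/0.70 = 0.79 (an assumed 45% vs 30% decrease) with 90 per arm: median test 31–41%, Mann-Whitney 47–59%, unadjusted robust Poisson 53–64%, Poisson adjusted for log prior-year count 56–75%.
- At the stated effect (ratio 0.571) with 68 per arm (90 × 0.75, rounded up): median test 83–89%, Mann-Whitney 95–98%, adjusted Poisson 99%. Over the unadjusted Poisson model, adjustment adds at most 2 points.

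Lower assumed rates reduce these powers, but the adjusted model stays at or above the others. The simulations omit the two-event entry route.

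**The case against.** A reader might infer that the primary outcome is a change from the prior year and that the trial's result is therefore biased. The documents do not support that. No section names the prior year as the reference. The objective is a comparison with placebo, and Protocol 8.1 gives the primary outcome as a number of exacerbations (there limited to infectious episodes). The eligibility count is an entry threshold, not a stated baseline, and Protocol 6.1 also quotes the GOLD definition. No planned analysis subtracts or divides by an earlier count. The wider on-trial definition applies to both randomised arms alike.

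It would also be wrong to say that adjustment is planned only if imbalance is found. Protocol 10.1 reads that way, but SAP 7.1.7 and 7.4.1 plan a covariate-adjusted Poisson model without that condition. On-trial events are to be diagnosed by the clinician, and patients attend when they have symptoms, which limits untreated home events and favours a high f. The scale in Protocol 5.6 governs temporary interruption of treatment and does not define the primary count.

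All of this stands, and it confines the point to the sizing assumption, within-group descriptions and the choice of primary estimator. It does not supply the missing reference. A reading of decrease as simply lower than placebo cannot explain a 30% decrease on placebo.

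**Conclusion.** The point holds in limited form and should be fixed before the analysis.

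- The reference for the decrease is undefined. On the only pre-entry count available, the two periods use different event definitions. With f between 0.90 and 0.70 (assumed), the 30% placebo decrease would appear as anything from 22% to none, and the 60% as 56% to 43%. The direction follows from the documents; the size rests on f.
- The randomised comparison of on-trial counts is not biased by this.
- The SAP leaves open which analysis is primary, and neither document names the prior-year count as a covariate. The gain from the adjusted model is clear against the median or Mann-Whitney test at a rate ratio near 0.79, and small at the stated 60% vs 30%. These powers depend on the assumed rates and variances.

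**What to change.** 1. Define the primary effect as the between-arm ratio of exacerbation rates over months 0–12. Estimate it with the robust Poisson model already planned (or negative binomial), with follow-up time as exposure and log prior-year exacerbation count as a named covariate whether or not the arms differ on it.
2. Keep the median or Mann-Whitney test as supportive, and make SAP 7.1.7, 7.1.9 and 7.4.1 agree.
3. Restate the sample-size assumption as an expected rate per arm with a stated dispersion.
4. Report events that meet the eligibility definition separately, and use only those for any before/after description. Reconcile the meaning of moderate in the eligibility criteria with that in Protocol 5.6, so that the label is unambiguous in the report.

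The cost is SAP wording plus the exact prior-year count for each patient. Eligibility needs only a threshold, and Table 1 does not list the count as a separate item, so it would have to be taken from the medical history or the records used to confirm eligibility. No change to treatment, visits or sample size is needed.
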